8.10.2 Management of Hematologic Toxicities

Background: Grade 3 or 4 neutropenia and febrile neutropenia occurred in 41% (98/240) and 5% of patients treated with venetoclax, respectively. Dosage adjustments of venetoclax due to adverse reactions occurred in 9.6% of patients. The most frequent adverse reactions leading to dose adjustments of venetoclax were neutropenia, febrile neutropenia, and thrombocytopenia. Most hematological toxicities AEs were first reported in the initial months of treatment of venetoclax, with highest incidence and prevalence of AEs in the first month and decreasing with time on study (Davids et al., 2016). Moreover, autoimmune hemolytic anemia (AIHA) and anemia were reported among the most frequent serious adverse reactions ($\geq 2\%$). The most frequent adverse reactions leading to drug discontinuation were thrombocytopenia and AIHA.

Serious infections including events of sepsis with fatal outcome have been reported in patients treated with venetoclax.

Treatment-emergent Grade 3 or 4 neutropenia occurred in 7% of MOR00208-treated patients in a phase I clinical trial in R/R CLL. There was one CLL patient treated with MOR00208 who experienced DLT of Grade 4 neutropenia lasting ≥ 7 days with febrile neutropenia in a phase I clinical trial of R/R CLL.

Management: Interrupt venetoclax and MOR00208 at 1st occurrence of Grade 3/4 neutropenia with infection or fever, or Grade 4 hematologic toxicities (except lymphopenia). Once the toxicity has resolved to Grade 1 or baseline level, venetoclax and MOR00208 therapy may be resumed at the same dose of venetoclax.

At 2nd and subsequent occurrences interrupt venetoclax and MOR00208. Consider transfusion and growth factor support as clinically indicated in accordance with institutional guidelines. Follow dose reduction guidelines in [Table 6](#) when resuming treatment with venetoclax after resolution. A larger dose reduction may occur at the discretion of the physician, but not below 100 mg daily dose after the ramp-up phase.

At 2nd and subsequent occurrences withhold MOR00208 and may resume as follows:

- Neutropenia: monitor ANC at least weekly until $ANC \geq 0.5 \times 10^9/L$ and/or neutropenic fever or infection is resolved
- Thrombocytopenia: monitor platelet count at least weekly until platelet count reach $\geq 25 \times 10^9/L$
- Anemia: monitor at least weekly until Grade 3

Thereafter, may resume as per protocol.

Patients should be advised to contact their doctor immediately if they develop a fever or any signs of infection.

Testing for AIHA (e.g. direct Coombs test, reticulocyte count) should be performed in patients receiving venetoclax treatment in accordance with institutional guidelines if AIHA is suspected of any grade.

Measures including antimicrobial therapy for any signs of infection including sepsis should be considered.

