Table 8: Guidance for Study Drug (Idelalisib/MOR00208) Dose Modifications Based on Type and Severity of Treatment-Emergent Adverse Events or Laboratory Abnormalities

NCI CTCAE Grade	Recommendation	
	Idelalisib	MOR00208
HEMATOLOGICAL ADVERSE EVENTS		
Neutropenia		
Grade 2 ($<1.5-1.0 \times 10^9/L$)	Maintain current dose level and schedule.	Maintain dosing as per protocol.
Grade 3 ($<1.0-0.5 \times 10^9/L$)	Maintain current idelalisib dose level and schedule. Monitor ANC at least weekly. Consider growth factor support.	Maintain dosing as per protocol. Monitor ANC at least weekly. Consider growth factor support.
Grade 4 ($<0.5 \times 10^9/L$) or occurrence of neutropenic fever or infection	Withhold idelalisib and monitor ANC at least weekly until ANC $\geq 0.5 \times 10^9/L$ and/or neutropenic fever or infection is resolved. Thereafter may resume idelalisib at lower (100 mg BID) dose at Investigator's discretion. Consider growth factor support.	Withhold MOR00208 and monitor ANC at least weekly until ANC $\geq 0.5 \times 10^9/L$ and/or neutropenic fever or infection is resolved. Thereafter, may resume as per protocol. Consider growth factor support.
Thrombocytopenia		
Grade 2 ($<75-50 \times 10^9/L$)	Maintain current dose level and schedule.	Maintain dosing as per protocol.
Grade 3 ($<50-25 \times 10^9/L$)	Maintain current dose level and schedule. Monitor platelets at least weekly.	Maintain dosing as per protocol. Monitor platelets at least weekly.
Grade 4 ($<25 \times 10^9/L$)	Withhold idelalisib until platelet count reach $\geq 25 \times 10^9/L$. Consider transfusion support. Monitor platelets at least weekly. May resume idelalisib at lower (100 mg BID) dose level when platelet counts have returned to $\geq 25 \times 10^9/L$.	Withhold MOR00208 until platelet count reach $\geq 25 \times 10^9/L$. Consider transfusion support. Monitor platelets at least weekly. Thereafter, may resume dosing as per protocol.
Anemia		
Grade ≥ 3 (Grade 3 defined as: Hemoglobin <8.0 g/dL; <4.9 mmol/L; <80 g/L; transfusion indicated)	Maintain dosing as per protocol. Consider transfusion and growth factor support in accordance with institutional guidelines.	Maintain dosing as per protocol. Consider transfusion and growth factor support in accordance with institutional guidelines.

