8.9.6 Management of Hematological and Immunological Events

Neutropenia

Background: Treatment-emergent Grade 3 or 4 neutropenia occurred in 31% of idelalisib-treated patients across clinical trials and in 7% of MOR00208-treated patients in a phase I clinical trial in R/R CLL. There was one CLL patient treated with MOR00208 who experienced DLT of Grade 4 neutropenia lasting ≥ 7 days with febrile neutropenia in a phase I clinical trial of R/R CLL.

Management: Blood counts including absolute neutrophil count (ANC) should be monitored at least every 2 weeks during the first 6 months of therapy with idelalisib, and at least weekly in patients while neutrophil counts are less than $1.0 \times 10^9/L$.

In the event of a **Grade 4** neutropenia ($< 0.5 \times 10^9/L$) idelalisib treatment and MOR00208 administration must be withheld. ANC should be monitored at least weekly until ANC $\geq 0.5 \times 10^9/L$ and/or neutropenic fever or infection is resolved. Thereafter, idelalisib treatment may be resumed at lower dose (100 mg BID) at the Investigator's discretion and MOR00208 treatment may be resumed as per protocol. Growth factors support can be considered.

Thrombocytopenia

Background: Treatment-emergent Grade ≥ 3 thrombocytopenia occurred in idelalisib-treated patients across clinical trials and in 7% of MOR00208-treated patients in a phase I clinical trial in R/R CLL.

Management: Platelet count should be monitored at least weekly if platelet counts are $< 50 \times 10^9/L$. In the event of a **Grade 3** thrombocytopenia ($< 50-25 \times 10^9/L$) idelalisib dose and MOR00208 administration should be maintained. In the event of a **Grade 4** thrombocytopenia ($< 25 \times 10^9/L$) idelalisib treatment and MOR00208 administration must be withheld until platelet counts reach $\geq 25 \times 10^9/L$. Transfusion support can be considered. When platelet counts have returned to $\geq 25 \times 10^9/L$, idelalisib treatment may be resumed at lower dose (100 mg BID) and MOR00208 treatment may be resumed as per protocol.

Anemia

Background: There was no serious AE related to MOR00208 treatment reported in CLL patients.

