8.9.8 Teratogenicity

Embryo-fetal toxicity, pregnancy and lactation

Based on findings in animals, idelalisib may cause fetal harm when administered to a pregnant woman. Therefore, fertile males and females of childbearing potential should abstain from sexual intercourse or use highly effective contraception (see [Appendix F](#)) while taking idelalisib and for 3 months after stopping treatment. If a female patient becomes pregnant or decides to breastfeed during the course of the study, all study therapy must be discontinued.

8.10 Guidance for Managing Specific Adverse Events for the combination of MOR00208 and Venetoclax

Recommendations for managing specific adverse events (based on the FDA Prescribing Information) are summarized in [Table 9](#).

Table 9: Recommended Dose Modifications for Toxicities

NCI CTCAE Grade ^a	Occurrence	Action	
		Venetoclax	MOR00208
Tumor Lysis Syndrome			
All Grades (Blood chemistry changes or symptoms suggestive of TLS)	Any	Withhold the next day's dose of venetoclax. If resolved within 24 to 48 hours of last dose, resume venetoclax at the same dose.	Maintain MOR00208 dosing as per protocol.
		For any blood chemistry changes requiring more than 48 hours to resolve, resume venetoclax at a reduced dose.	
		For any events of clinical TLS, ^b resume venetoclax at a reduced dose following resolution.	Withhold MOR00208 for any events of clinical TLS ^b . After resolution MOR00208 therapy may be resumed at the discretion of the physician.
Non-Hematologic Toxicities			
Grade 3 or 4 non-hematologic toxicities	1 st occurrence	Interrupt venetoclax. Once the toxicity has resolved to Grade 1 or baseline level, venetoclax therapy may be resumed at the same dose. No dose modification is required.	Interrupt MOR00208. Once the toxicity has resolved to Grade 1 or baseline level, MOR00208 therapy may be resumed.

NCI CTCAE Grade ^a	Occurrence	Action	
		Venetoclax	MOR00208
	2 nd and subsequent occurrences	Interrupt venetoclax. Follow dose reduction guidelines in Table 6 when resuming treatment with venetoclax after resolution. A larger dose reduction may occur at the discretion of the physician, but not below 100 mg daily dose after the ramp-up phase.	Interrupt MOR00208. After resolution MOR00208 therapy may be resumed at the discretion of the physician.
Hematologic Toxicities			

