Grade 3 or 4 neutropenia with infection or fever or Grade 4 hematologic toxicities (except lymphopenia)	1 st occurrence	Interrupt venetoclax. To reduce the infection risks associated with neutropenia, granulocyte-colony stimulating factor (G-CSF) may be administered with venetoclax if clinically indicated. Once the toxicity has resolved to Grade 1 or baseline level , venetoclax therapy may be resumed at the same dose.	Interrupt MOR00208. To reduce the infection risks associated with neutropenia, granulocyte-colony stimulating factor (G-CSF) may be administered with MOR00208 if clinically indicated. Once the toxicity has resolved to Grade 1 or baseline level , MOR00208 therapy may be resumed.

MorphoSys AG Proprietary Information

NCI CTCAE Grade ^a	Occurrence	Action	
		Venetoclax	MOR00208
	2 nd and subsequent occurrences	Interrupt venetoclax. Consider transfusion and growth factor support as clinically indicated in accordance with institutional guidelines. Follow dose reduction guidelines in Table 6 when resuming treatment with venetoclax after resolution. A larger dose reduction may occur at the discretion of the physician, but not below 100 mg daily dose after the ramp-up phase.	Interrupt MOR00208. Consider transfusion and growth factor support as clinically indicated in accordance with institutional guidelines. MOR00208 therapy may be resumed after resolution, as follows: Neutropenia: Withhold MOR00208 and monitor ANC at least weekly until ANC $\geq 0.5 \times 10^9/L$ and/or neutropenic fever or infection is resolved. Thereafter, may resume as per protocol. Thrombocytopenia: withhold MOR00208 until platelet count reach $\geq 25 \times 10^9/L$ and monitor at least weekly. Thereafter, may resume as per protocol. Anemia: Withhold MOR00208 until Grade 3 and monitor at least weekly. Thereafter, may resume as per protocol.

Consider discontinuing venetoclax for patients who require dose reductions to less than 100 mg for more than 2 weeks during the ramp-up phase. Dose modifications below 100 mg are not allowed after the ramp-up phase and patient should discontinue venetoclax treatment.

^aAdverse reactions were graded using NCI CTCAE version 4.03.

^bClinical TLS was defined as laboratory TLS with clinical consequences such as acute renal failure, cardiac arrhythmias, or sudden death and/or seizures.

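### The neutropenia restart rule joins count recovery and fever resolution with and/or; read as or, it contradicts the hold triggers in the same rows

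*Protocol*

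**What the plan says.** **Cohort A.** Table 8 (Section 8.9) withholds both drugs for Grade 4 neutropenia (ANC below 0.5 x 10^9/L) "or occurrence of neutropenic fever or infection". The MOR00208 column ends the hold at an ANC of 0.5 or higher "and/or neutropenic fever or infection is resolved. Thereafter, may resume as per protocol". The idelalisib column uses the same joining words, then allows 100 mg twice daily at the investigator's discretion. Section 8.9.6 covers the same event in prose but names only Grade 4 neutropenia as the trigger: "idelalisib treatment and MOR00208 administration must be withheld. ANC should be monitored at least weekly until ANC" is at least 0.5, followed by the same and/or clause and permission to resume both drugs.

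**Cohort B.** Table 9 (Section 8.10) and Section 8.10.2 interrupt both drugs for Grade 3 or 4 neutropenia with infection or fever, and for Grade 4 hematologic toxicity other than lymphopenia. The first event has a strict release: "Once the toxicity has resolved to Grade 1 or baseline level, venetoclax and MOR00208 therapy may be resumed at the same dose of venetoclax". From the second event, Table 9 states that "MOR00208 therapy may be resumed after resolution, as follows", and its neutropenia line is again ANC of at least 0.5 "and/or neutropenic fever or infection is resolved". Section 8.10.2 repeats it. Venetoclax at repeat events follows the dose steps of Table 6 after resolution, without the and/or clause.

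Neither document says that both conditions must hold. The SAP does not deal with restart rules.

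**The concern.** A hold rule has to tell every site the same thing about the same patient. Here a site reading *and* keeps holding a patient who is still febrile or whose ANC is still below 0.5. A site reading *or* may restart.

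The safety background is in the protocol. Section 8.9.4 reports serious and fatal infections with idelalisib. On venetoclax, Section 8.10.2 states: "Serious infections including events of sepsis with fatal outcome have been reported in patients treated with venetoclax". The phase I study of MOR00208 had one dose-limiting toxicity, which was prolonged Grade 4 neutropenia with febrile neutropenia (Section 8.6, Table 2). The primary endpoint is the incidence and severity of adverse events in about 12 patients per cohort, so inconsistent dosing of even one such patient would be visible in the results.

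**Working it through.** The plan gives no figure to reproduce, so the check sets release wording against hold trigger for each clinical state. Grade limits come from Table 8: Grade 3 is ANC 0.5 to below 1.0, Grade 4 is below 0.5. The last three columns ask whether the condition that started the hold is still present.

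| ANC (x 10^9/L) | Fever or infection | Released under *and* | Released under *or* | Table 8 trigger | Table 9 trigger | 8.9.6 trigger |
|---|---|---|---|---|---|---|
| 1.0 or higher | resolved | yes | yes | no | no | no |
| 0.5 to <1.0 | resolved | yes | yes | no | no | no |
| 1.0 or higher | continuing | no | yes | unclear | no | no |
| 0.5 to <1.0 | continuing | no | yes | yes | yes | no |
| <0.5 | resolved | no | yes | yes | yes | yes |
| <0.5 | continuing | no | no | yes | yes | yes |

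- **Rows 4 and 5.** Under *or*, Tables 8 and 9 permit restart in a state that their own trigger still tells the site to hold. This is a direct contradiction within a row.
- **Row 3.** ANC has recovered but fever or infection continues. Table 9's neutropenia trigger has lapsed. Table 8 does not say whether a fever still counts as neutropenic at this count. The *or* reading releases the patient and no trigger clearly stops it.
- **Section 8.9.6.** In rows 3 and 4 its only trigger, Grade 4 neutropenia, has lapsed, so on its own text nothing opposes restart in a febrile patient. It also disagrees with Table 8 on when to hold at all.

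Other provisions narrow the gap without closing it:

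- Section 8.6 has a stricter general rule for MOR00208, but only for toxicities not described in Tables 8 and 9 or Sections 8.9 and 8.10.
- Section 8.7 requires severe or life-threatening idelalisib-related toxicity to resolve, but covers idelalisib only.
- Table 9's row for "Grade 3 or 4 non-hematologic toxicities" would catch a severe infection, but in Cohort B only.
- Table 8's serious-infection rows cover PJP and CMV only.

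**How soon it could matter.** Section 8.1.1 gives 3 x 4 + 1 = 13 infusions in the first 84 days, so the next scheduled dose is at most 7 days away. Later intervals are 14 days (Cycles 4 to 6) and 28 days (from Cycle 7).

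**How often the situation might arise.** The documents give no rate for these combinations. As an assumption, take 1/27 = 3.7% from the MOR00208 phase I case (Table 2) and 5% from Section 4.3, where febrile neutropenia is among the serious events at 5% or more with idelalisib plus rituximab. The chance of at least one affected patient in 12 is 1 - (26/27)^12 = 36%, or 1 - 0.95^12 = 46%. That is the chance that a first febrile neutropenia occurs, which is the relevant count for Cohort A. It is not the chance of a wrong restart.

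**The case against.** The strongest reply is that the trigger column already settles the matter. A patient at ANC below 0.5 is still Grade 4, and a febrile patient at 0.5 to below 1.0 still has neutropenic fever, so both are still to be held. Because the trigger is itself a choice between low count and fever or infection, and/or in the release can naturally mean whichever condition caused the hold, or both. This stands as a plausible reading. But the text does not say so, and it does not fit Section 8.9.6, where fever and infection are not triggers. It also leaves open the patient held for a low count who develops fever before the count recovers.

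In Sections 8.9.6 and 8.10.2 the word *until* governs ANC monitoring rather than the hold. That is correct, but permission to resume follows directly from the same condition, and in both tables *until* covers withholding as well.

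The safeguards are real. Restart is permissive. Body temperature is taken immediately before each infusion (Section 9.3.2.2). The local panel includes ANC, is scheduled at every infusion visit and is reviewed before dosing (Tables 10 and 11, Section 9.3.2.5). In Cohort B, neutropenia of Grade 3 or higher with infection or fever is an event of special interest reported within 24 hours (Sections 10.1 and 10.5). These make an unsafe restart unlikely, but they do not tell the site which reading is intended.

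**Conclusion.** The restart wording is ambiguous and, read as *or*, contradicts the triggers beside it. The exposure is greatest under Section 8.9.6 and for patients whose ANC has recovered while fever or infection continues. It covers both drugs from the first event in Cohort A, though Section 8.7 leaves less room for idelalisib, and MOR00208 only, from the second event, in Cohort B. The importance is moderate: a cheap safety correction, not a defect that undermines the trial. This rests on restart staying optional and on the pre-infusion checks being done as written.

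A reader might go further in three ways that the documents do not support.

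- One might say that *or* frees the patient in most states, or that a hold for Grade 3 neutropenia with fever is empty from its first day. That ignores the trigger column, which still orders the hold.
- One might infer that patients will be restarted unsafely in some number. None can be derived.
- One might call the looser count threshold at repeat events in Cohort B an error. It matches the MOR00208 threshold in Cohort A and may be deliberate.

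**What to change.** In both drug columns of Table 8, in Section 8.9.6, in Table 9 and in Section 8.10.2, replace *and/or* with *and, if present,* and leave the rest of each sentence as it is. In Section 8.9.6, add Table 8's second trigger, "or occurrence of neutropenic fever or infection", so that text and table agree. The ANC threshold of 0.5 and the repeat-event levels in Cohort B stay unchanged.

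The cost is a protocol amendment and slightly longer holds for a few patients. Section 13.7.1 treats clarifications as administrative only if patient safety is unaffected. The sponsor could argue this if *and* was always meant, but since the change concerns a safety dosing rule it is prudent to plan for a substantial amendment. Longer holds should rarely end treatment: Section 8.11 leads to the end-of-treatment visit only when both drugs are interrupted for more than 28 days for the same toxicity judged related to both.

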8.10.3 Management of Teratogenicity

Embryo-fetal Toxicity, Pregnancy and Lactation

Based on its mechanism of action and findings in animals, venetoclax may cause embryofetal harm when administered to a pregnant woman. In an embryo-fetal study conducted in mice, administration of venetoclax to pregnant animals at exposures equivalent to that observed in patients at the recommended dose of 400 mg daily resulted in post-implantation loss and decreased fetal weight. There are no adequate and well-controlled studies in pregnant woman using venetoclax. Advise females of reproductive potential to avoid pregnancy during treatment. If venetoclax is used during pregnancy or if the patient becomes pregnant while taking venetoclax, the patient should be apprised of the potential hazard to the fetus.

Pregnancy - Risk Summary

There are no available human data on the use of venetoclax in pregnant women. Based on toxicity observed in mice, venetoclax may cause fetal harm when administered to pregnant women. In mice, venetoclax was fetotoxic at exposures 1.2 times the human clinical exposure based on AUC at the recommended human dose of 400 mg daily. If venetoclax is used during pregnancy or if the patient becomes pregnant while taking venetoclax, the patient should be apprised of the potential risk to a fetus. The background risk in the general population of major birth defects is 2% to 4% and of miscarriage is 15% to 20% of clinically recognized pregnancies.

Animal data. In embryo-fetal development studies, venetoclax was administered to pregnant mice and rabbits during the period of organogenesis. In mice, venetoclax was associated with increased postimplantation loss and decreased fetal body weight at 150 mg/kg/day (maternal exposures approximately 1.2 times the human AUC exposure at the recommended dose of 400 mg daily). No teratogenicity was observed in either the mouse or the rabbit.

Lactation - Risk Summary

There are no data on the presence of venetoclax in human milk, the effects of venetoclax on the breastfed child, or the effects of venetoclax on milk production. Because many drugs are excreted in human milk and because the potential for serious adverse reactions in breastfed infants from venetoclax is unknown, advise nursing women to discontinue breastfeeding during treatment with venetoclax.

Females and Males of Reproductive Potential

Venetoclax may cause fetal harm. Females of reproductive potential should undergo pregnancy testing before initiation of venetoclax. Advise females of reproductive potential to use effective contraception during treatment with venetoclax and for at least 30 days after the last dose. Based on findings in animals, male fertility may be compromised by treatment with venetoclax.

8.11 Rules for Permanent Stop of Study Medication Intake

If treatment needs to be interrupted for ≤ 28 days for drug-related toxicity of the same study drug (idelalisib or venetoclax or MOR00208), treatment should continue at the next protocol scheduled visit whenever possible. Missing visits or doses of either drug should not be made up for, with exception for the make up of a missed MOR00208 dose during the monthly MOR00208 treatment, as described in Section 8.12.

If treatment with one study drug needs to be interrupted for >28 days for the same, persistent, drug-related toxicity, the patient should continue to be dosed with the other study drug, as per protocol.

If treatment with both study drugs needs to be interrupted for >28 days for the same persistent study drug-related toxicity, judged by the Investigator to be related to both study drugs (idelalisib/venetoclax and MOR00208), then the End of Treatment (EOT) visit will be performed and the patient will enter the follow-up period.

